#### 2.0 Aims and Objectives

#### 2.1 Aim

To identify what factors contribute to variation in, and influence, clinicians' decision making about intravenous thrombolysis for acute ischaemic stroke, given what is already known about the most effective and safe use of the treatment, in order to inform programmes that seek to influence clinical behaviour and decision-making.

#### 2.2 Objectives

(i) to determine which patient factors influence clinical decision making about the offer of thrombolysis;

(ii) to identify and quantify the trade-offs clinicians make regarding the decision to offer thrombolysis;

(iii) to determine which clinical factors influence clinical decision making about the offer of thrombolysis (e.g. clinician experience, setting, personality type);

(iv) to influence clinicians' behaviour by translating learning into continuing professional development activity, national clinical guidelines, supporting implementation of an existing thrombolysis decision support tool, and informing clinical audit and evaluation programmes (SSNAP).

The study will capture information on medical judgement and choice to illuminate the decision making processes underpinning clinicians' willingness to offer thrombolysis with the overall aim of optimising care for acute stroke patients by better supporting risk communication, consent and decision-making with patients and their families.

#### 3.0 Methods

#### 3.1 Study Design

DCEs explore the trade-offs between competing factors within decision making by eliciting participants' preferences and the relative importance of those factors [9, 37]. The DCE will be conducted with stroke physicians and neurologists in secondary care and specialist stroke centres and will involve the following stages:

## 3.2 Exploratory work to establish factors influencing decision making (determining attributes & levels)

In depth exploratory work, usually involving qualitative methods and literature review, is an important first stage in a DCE to establish the attributes (characteristics of the decision making model) and levels (magnitude of those characteristics)[44]. Much of this background exploratory work, which is essential to the design of a high quality DCE, has already been undertaken as part of a NIHR programme grant[34]. We will draw on previously completed work by the project team, including existing qualitative interview data on the views and experiences of stroke clinicians about thrombolysis decision making, as well as ethnographic data collected through non participant observation and data from the usability testing of the DASH decision support tool[18, 34, 45]. Systematic review of these data will identify key influences on decision making to inform the experimental design of the DCE and will enhance external validity. We already have evidence on the broad range of patient attributes that are important (such as age, gender, history of stroke, severity of stroke (NIHSS score); stroke onset time to treatment, systolic blood pressure; diabetes; history of hypertension; blood glucose; recent infarction on CT/MRI scan; aspirin monotherapy; and aspirin plus clopidogrel) but will undertake additional qualitative interviews with non-expert clinicians (defined here as recently appointed stroke consultants) to determine the appropriate set and levels of attributes. The value of interviewing non-expert clinicians is that they may be more likely to make explicit certain aspects of decision making that a more expert clinician could take for granted and may fail to disclose.

Face-to-face, semi-structured interviews will be conducted with up to ten non-expert clinicians; these will be audio-recorded and transcribed verbatim. Our sampling strategy will be purposive to

include clinicians from the local cardiovascular network and beyond. Because thrombolysis rates are relatively high in the North East of England, we will also approach clinicians from another cardiovascular network with lower rates of thrombolysis, (based on figures from national audit reports). We will recruit five clinicians locally and five from other networks; the latter will be interviewed by telephone. Participants will be asked to reflect on their clinical experience where thrombolysis was considered, in particular they will be asked to think back to grey/borderline/difficult cases and to talk through the decision making process, trade-offs made and influencing factors. Additional prompts will include: influential factors beyond guidelines and licensing criteria; experiences of adverse events; communicating risks and benefits of thrombolysis; attitude to risk; colleagues' views and experiences; and approaches and norms within practice setting. Anonymised transcripts will be coded thematically and analysed using a framework approach[46] to establish the range of attributes (and levels) to be included in the DCE. This will be particularly important for possible 'grey' areas, such as age, where age > 80 years is a contraindication in the licensing criteria but arguments have been made that physiological/functioning age is more important than chronological age[47]. Special consideration will be given to patient factors that are not part of the underlying predictive model, such as social circumstances and prior functional status, together with other factors that may the incorporated or influence clinical decision-making (for example, better clinical expertise and perceptions of the evidence base). In short, these interviews will be used to identify any additional patient attributes and clinician related factors that might influence decision-making that are not accounted for in our existing qualitative data.

**3.3 Experimental Design:** A fractional factorial design will be used to combine attributes and levels to construct hypothetical patient scenarios, in the form of vignettes. The narrative format of vignettes, rather than the traditional tabular lists of attributes and levels, will be used in order to increase participant engagement[48]. For each vignette, participants will be asked whether they would offer treatment or not, rather than making a choice between two different case vignettes. To enhance validity, all scenarios will be discussed with stroke physicians in the study advisory group to ensure that they are plausible and clinically appropriate, and provide an appropriate range and variety of cases. To enhance validity (and allow comparison of model predictions to actual choices), a subsection of vignettes will be based, as closely as possible, on real cases identified through SITS-UK (thrombolysed cases only)[49] and a database of anonymised cases (both treated and non-treated) collected as part of local audit. Vignettes will include CT scans to make the scenarios as close to actual clinical situations as possible. Importantly, our experimental design will allow us to include a number of vignettes that show variation in patient factors that are likely to be most sensitive to differing decisions, that is those difficult, 'grey zone' cases.

**3.4 Development of DCE survey**: The vignettes will be reduced to a manageable number using experimental design techniques (fractional factorial design) and incorporated into a survey. Within the survey the case vignettes will be preceded by a series of questions on possible covariates such as clinician age, grade/seniority, experience with rtPA, experience of adverse events associated with use of thrombolysis, personality type/risk aversion (using the Jackson Personality Inventory Risk-taking subscale[19, 39]).

**3.5 Programming of online version of the survey**: The DCE will be programmed into an online survey to enhance ease and speed of survey dissemination (for efficiency purposes this will be outsourced to an independent company). The survey will be designed to be short, straightforward and easy to complete; usability issues will be assessed during the piloting stage.

**3.6 Pilot DCE**: The survey will be pretested, with a convenience sample of up to eight clinicians, to establish the clinical validity of the vignettes, examine participants' understanding and check how long the survey takes to complete[50]. This will address practical issues, such as length of the survey to avoid response fatigue[10, 37], optimal presentation of choice sets, and views on how to make the website easier to use[10]. Pretesting will include a think aloud approach[51], using a subset of vignettes, to facilitate adaptation of the survey instrument.

#### 12/5001/45

3.7 Data collection and Sampling: We will recruit clinicians via the British Association of Stroke Physicians (BASP, total sample size n=350) and aim to maximise response rate with reminders at two and four months. An invitation to participate, together with an information sheet, will be distributed to members of BASP with a link to the online survey. CP, who is a member (and exchair) of the BASP Training and Education Committee, will facilitate this approach. Whilst sampling through BASP will capture the great majority of decision makers on thrombolysis in the UK, we will extend our sample by inviting members of the BASP trainees' group to participate (once again facilitated by CP). To increase numbers and broaden representation, we also plan to circulate the invitation nationally via the cardiovascular network. To take account of diversity in how services are delivered (i.e. in some cases emergency department (ED) specialist physicians may have independent responsibility for decision making about thrombolysis), we will also distribute the invitation to participate via the Society for Acute Medicine to include ED specialists with responsibilities for thrombolysis. Importantly eligibility for participation in the survey will be defined as the potential participant having independent responsibility for decision making about thrombolysis. ED specialists involved only in discussions about the offer of thrombolysis will be excluded. To ensure that these criteria are adhered to, a question about the respondent's role in decision making will be included in the introductory questions of the survey.

Optimal sample size requirements for the limited dependent variable models of the nature estimated in DCEs depend on knowledge of the true choice probabilities, which are not known prior to undertaking the research[52]. However, previous DCE studies have shown that robust choice models can be estimated from sample sizes between 50-100 respondents.[53, 54]. Each clinician will be presented with up to 16 vignettes.

#### 3.8 External Validity

High levels of external validity have been demonstrated in DCEs in a number of areas in which DCEs have been applied, including in health, environment, and transport settings[52, 55]. For example, in a study of physicians' prescribing decisions, stated preference responses to hypothetical scenarios were shown to align with revealed preference (i.e. preferences under simulated conditions aligned with actual behaviour)[55]. Our approach to ensuring high levels of external validity in this study is multi-fold. First, we will draw upon existing evidence from interview and ethnographic work to identify the full range of attributes (and levels) likely to influence decision making. Second, we will design the choice set to mimic as closely as possible the decision of interest. This will be in the form of a binary choice (decision to offer thrombolysis or not), as this reflects clinical practice in that clinicians are faced with one patient at a time and must decide whether or not to offer thrombolysis. Similarly vignettes (as opposed to a traditional tabular list of attributes and levels that are commonly used in DCEs) more closely reflect the way in which clinicians receive information about their patients, thereby increasing the realism of the decision Clinicians tend to be familiar (and likely more comfortable) with vignettes as they are task. regularly used in training and continuing professional development. Consequently, participating clinicians are unlikely to treat the exercise as a test and thus behave differently to how they would in the real world. That said, we will make it clear in the information sheet preceding the DCE survey that all responses will be anonymised and individuals will not be judged on their responses against guideline/licensing criteria. The importance of honest, 'uncensored' responses will be reiterated in information about the survey, as well as within the survey instrument itself. Furthermore, we will undertake in-depth pilot work to establish the clinical face and content validity, and ease of understanding and accessibility of the vignettes. The clinical members of the research team will be further involved in this important component to ensure that the vignettes in the final survey are acceptable to clinicians and possess maximal clinical face/content validity.

Stated preferences to offer/withhold thrombolysis for patients in hypothetical scenarios in the DCE will be compared with thrombolysis decisions in actual practice settings (using anonymised cases identified through local audit data (both treated and non-treated cases) and patient registries such as SITS-UK (treated cases only)[49]

#### 12/5001/45

#### 3.9 Data Analysis

The data will be modelled in a random utility theory framework using limited dependent variable modelling. The decision to offer thrombolysis will be modelled as a function of the attributes of the hypothetical patient and the characteristics of the decision makers. This will allow investigation of which characteristics of the patients have a positive effect and which have a negative effect on the decision to offer thrombolysis, as well as which characteristics of the decision makers (e.g. age, experience of offering thrombolysis, attitudes to risk etc.) have a positive or negative impact on the decision to offer thrombolysis. Heterogeneity will be explored using random coefficients and scale-adjusted latent class modelling. Using the preferred model (based on goodness of fit criteria such as Akaike or Bayesian information criterion)[17], marginal rates of substitution will be calculated to quantify the rate at which decision makers are prepared to trade off one attribute for another, which also allows investigation of the relative importance, or ranking, of the characteristics of patients to the decision to offer thrombolysis[44]. Predicted probability analysis will investigate the probability of offering thrombolysis using clinically relevant values on the attribute levels.

Ideally, as part of our analyses, we would like to compare the characteristics of responders with non-respondents to detect the possibility of non-response bias. However, the possibility of such comparisons is limited as BASP do not collect demographic information about their members. Concerns about response bias will depend on overall response rates. In a previous survey conducted by one of our co-applicants and distributed though BASP a response rate of 72%[56] was achieved, indicating that a good response can be expected from clinicians with a specific interest in this area. We will design and develop the survey and invitations to maximise response rates based on best practice in survey design and drawing on the experiences of our co-applicants. In addition, we will fully describe the characteristics of responders to our survey which will allow an approximate assessment of whether or not the sample is representative of the wider population of physicians who make decisions about thrombolysis. We will also consult the Royal College of Physicians census data on the average age and gender of stroke physicians and emergency department specialists to assess the representativeness of our sample.

We will also model the population-level impact of patient-related attributes identified in the DCE as statistically significant drivers and inhibitors of decisions to offer thrombolysis, in terms of losses and gains in Quality Adjusted Life Years (QALYs) from treatment with and without thrombolysis.

QALYs for individual patients with specific attributes (stroke onset time to treatment, systolic blood pressure, diabetes, stroke severity, age, gender, prior stroke, signs of current infarction on pretreatment scan, blood glucose, aspirin and clopidogrel, aspirin monotherapy, weight and history of hypertension) are calculated in the DASH II decision analytic model as a function of modified Rankin values (functional independence, dependence and death) at three months and with reference to life tables with actuarial data on life expectancy in terms of absolute age. Patient-related attributes (and associated levels) identified as drivers and inhibitors in the DCE (e.g., gender [male, female) and 15 mm/Hg intervals in systolic blood pressure), which are also present in the DASH II decision analytic model[34], will be used to estimate how changing the levels across each patient-related attribute (holding other levels of attributes constant in the DASH II decision analytic model using the range of levels of attributes with thrombolysis in the SITS-UK database) impacts on QALY gains/losses for patients treated with and without thrombolysis. In addition, this method would be used to estimate the marginal cost-effectiveness of treating patients with and without the criterion identified in the DCE.

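### Section 3.9 promises a population-level QALY impact of the factors that drive the offer, but its method returns only per-patient QALYs by attribute level

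*Protocol*

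**What the plan says.** The last part of Protocol section 3.9 adds a QALY analysis to the choice modelling.

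- **Target.** "We will also model the population-level impact of patient-related attributes identified in the DCE as statistically significant drivers and inhibitors" of the offer, "in terms of losses and gains in Quality Adjusted Life Years (QALYs) from treatment with and without thrombolysis".
- **Source of QALYs.** QALYs for individual patients "are calculated in the DASH II decision analytic model as a function of modified Rankin values" at three months, together with life tables.
- **What comes from the DCE.** "Patient-related attributes (and associated levels) identified as drivers and inhibitors in the DCE", restricted to those that DASH II also contains.
- **Operation.** These attributes "will be used to estimate how changing the levels across each patient-related attribute", with the remaining attributes fixed and drawing on the range seen in SITS-UK, "impacts on QALY gains/losses for patients treated with and without thrombolysis".

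Two other statements bear on this. The first paragraph of section 3.9 plans marginal rates of substitution, a ranking of patient characteristics and predicted probabilities of offering thrombolysis, but nothing carries these into the QALY step. Sections 3.3 and 3.8 say that SITS-UK covers thrombolysed patients only, whereas the local audit data cover treated and untreated patients.

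**The concern.** The target and the method do not match. The population impact of a factor that influences the offer depends on three things: how many eligible patients have the factor, how far it changes the chance of an offer, and what treatment is worth to those patients. The stated method delivers only the third. DASH II could produce that without a DCE, once someone had named the attributes and levels.

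This is the one analysis that turns clinicians' preferences into consequences for patients. Section 4.0 sends the study's findings to training, the DASH II tutorial, national audit and possible guideline inclusion. If per-patient benefit by level is reported as population-level impact, those programmes may be pointed at attributes where treatment benefit is large but clinicians' behaviour hardly varies, and away from attributes that strongly suppress offers.

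Entry by statistical significance is a second, smaller weakness. Which attributes appear in the QALY analysis then depends partly on how many clinicians reply.

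**Working it through.** The plan states no figure for this analysis, so there is nothing to reproduce. The check is structural, followed by an illustration.

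**Step 1: what enters the calculation.**

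| Component of population impact | Present in the QALY method? |
|---|---|
| QALYs treated minus untreated, by level (dQ) | Yes, from DASH II |
| Attributes and levels to vary | Yes, from the DCE |
| Change in offer probability (dp) | No; predicted probabilities are planned separately |
| Number or share of eligible patients with the level | No; the only reference data named for this step are SITS-UK |

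**Step 2: what the omission does.** All inputs are assumptions: N = 1,000 eligible patients, 30% at the inhibiting level and the rest at the reference level, and baseline offer probability p0 = 0.70.

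dp = expit(logit(0.70) + beta) - 0.70

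Impact = N x 0.30 x dp x dQ

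With dQ = 0.3 QALY:

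| DCE coefficient (beta) | dp | Population impact (QALYs) | Planned output (QALY per patient) |
|---|---|---|---|
| -0.2 | -0.044 | -3.9 | 0.3 |
| -0.5 | -0.114 | -10.3 | 0.3 |
| -1.0 | -0.238 | -21.4 | 0.3 |
| -2.0 | -0.460 | -41.4 | 0.3 |

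For example, 1,000 x 0.30 x (-0.460) x 0.3 = -41.4. Impact differs about 10.5-fold from first to last row while the planned output does not move. Reporting the change in dQ between levels, instead of dQ at a level, makes no difference to this: beta appears in neither.

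**Step 3: ranking.** With the same N, share and p0:

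- Attribute A: dQ = 0.5, beta = -0.2. Impact -6.5 QALYs.
- Attribute B: dQ = 0.2, beta = -2.0. Impact 1,000 x 0.30 x (-0.460) x 0.2 = -27.6 QALYs.

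Per-patient benefit puts A first; population impact puts B first.

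**Step 4: the reference population.** If every offer led to treatment, the share of treated patients with an inhibiting level would be 0.30 x p1 / (0.30 x p1 + 0.70 x 0.70), where p1 = 0.70 + dp. A true share of 30% would appear as 28.7%, 26.4%, 22.0% and 12.8% for the four coefficients. A treated-only registry therefore under-represents the strongest inhibitors most.

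**Step 5: the significance rule.** Section 3.7 treats 50 to 100 respondents as enough and gives BASP as 350; section 3.9 cites a 72% response to an earlier survey, and 350 x 0.72 = 252. Assume a balanced two-level attribute with true odds ratio 1.2, 16 vignettes per clinician, offers near 50%, independent responses and a two-sided 5% test.

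SE(log OR) = sqrt(4 / (n x 16 x 0.25)) = 0.115 for n = 75 and 0.063 for n = 252.

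The chance of selection is 35% and 82%. The same true effect could well be left out or included, depending on the response.

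**The case against.** **The target could be read more modestly.** Section 3.9 qualifies the impact as QALYs with and without thrombolysis, and the study wants to know which influences on the offer are appropriate. For that question, benefit by attribute level is useful and needs no offer weight. This stands as a defence of the output, but not of its label: nothing in the method scales to a population.

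**Offer magnitude is not lost from the study.** The predicted probabilities and the ranking will show which inhibitors are weak and which strong. This is true, and a statistical analysis plan might combine them with the QALYs. But the protocol does not leave the step open; it specifies a method, and that method misses the stated target.

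**A reader might infer that significance selection biases the QALY figures.** Under the Step 5 assumptions, selected log odds ratios are inflated 1.67-fold (n = 75) or 1.11-fold (n = 252). But no coefficient enters the QALY calculation, so the inflation cannot reach it. Only the list of reported attributes is affected. Nor does the protocol state a significance level or say that unselected attributes have zero impact.

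**The weighted figure has weaknesses of its own.** An offer is not treatment, since section 1.0 requires consent. Vignette choices deliberately include borderline cases (section 3.3), and their agreement with practice is still to be tested (section 3.8). Untreated cases come only from local audit, in a region where section 3.2 says treatment rates are relatively high. All of this stands and must be stated with the result.

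**Marginal cost-effectiveness**, the last sentence of section 3.9, compares treated with untreated patients and needs no offer probability. It is unaffected.

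**Conclusion.** The point holds: the QALY method in section 3.9 does not estimate the population-level impact that the same section promises. It returns per-patient QALYs by attribute level for a set of attributes that depends partly on the response. Weak and strong inhibitors with the same DASH II benefit are not separated, and the ranking for population impact can be wrong.

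The size cannot be taken from the protocol. The 10.5-fold spread and the reversed ranking rest on the assumed share, baseline probability, coefficients and QALY gains; they show that the gap can be large, not how large it will be.

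Severity is moderate. The analysis is supplementary and lies outside objectives (i) to (iv) in section 2.2. It would be tempting to conclude that the DCE itself or its trade-off estimates are compromised. The document does not support that: the choice model, marginal rates of substitution and predicted probabilities do not depend on this step.

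**What to change.** Amend section 3.9 before analysis.

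1. For every DCE attribute that is also in DASH II, significant or not, define impact as the average over eligible patients of [P(offer at the actual level) - P(offer at a stated reference level)] x [DASH II QALYs with minus without thrombolysis]. Take the probabilities from the preferred choice model.
2. Average over treated and untreated eligible patients, for example the local audit cases, because SITS-UK lacks the untreated.
3. Carry coefficient uncertainty through, for example by simulating from the coefficient covariance matrix.
4. State the assumptions that an offer leads to treatment and that vignette probabilities approximate practice.
5. Drop statistical significance as the entry rule.

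If this is not wanted, reword the target to claim only per-patient QALY effects by attribute level.

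**Cost.** The first option needs new wording, some computing and audit records that carry the DASH II attributes; the protocol does not say whether they do. Intervals will be wider, some spanning zero, and results will depend on a local case mix and on stated preferences. The second option costs one sentence, but gives up the population-level claim.

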Potential physician-related factors that might influence consideration of thrombolysis have been posited, and include factors such as over-estimation of the rate of adverse effects (symptomatic intracranial haemorrhage) and uncertainty about the effectiveness of thrombolysis[7, 26]. The situation is further complicated by the absence of data on outcomes as a function of individual patient characteristics and lack of consensus on relative contraindications for thrombolysis[6, 31]. Whilst the licensing criteria provide broad eligibility guidance, they do not reflect variation within the criteria in terms of potential outcomes and adverse effects; although it is clear that these will vary from patient to patient (for example related to variations in blood pressure, age, stroke severity). As others have observed "managing uncertainty is central to clinical practice and requires the linking of experience and evidence: this places specialists at an advantage"[32](p.139). It is important, therefore, to understand how clinician factors such as level of expertise, age, seniority, practice setting, attitude to risk[19] etc. influence the decision to offer thrombolysis. Further, there is a paucity of available tools to support individualised decision making about thrombolysis and those tools that are currently widely available have limitations in terms of their risk communication

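### The QALY analysis is labelled population-level, but its one-attribute-at-a-time rule gives results conditional on the held values and does not average over patients

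*Protocol*

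**What the plan says.** Protocol section 3.9 (Data Analysis) states the aim: "We will also model the population-level impact of patient-related attributes identified in the DCE as statistically significant drivers and inhibitors" of the decision to offer thrombolysis, measured in QALYs gained or lost with and without treatment.

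The next paragraph of 3.9 gives the method. "QALYs for individual patients with specific attributes" are produced by the DASH II model "as a function of modified Rankin values (functional independence, dependence and death) at three months and with reference to life tables". Attributes found in the discrete choice experiment that are also DASH II inputs "will be used to estimate how changing the levels across each patient-related attribute" affects QALYs, while "holding other levels of attributes constant in the DASH II decision analytic model using the range of levels of attributes" among thrombolysed patients in SITS-UK. The same method then serves the marginal cost-effectiveness estimate.

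The listed inputs include "blood glucose, aspirin and clopidogrel, aspirin monotherapy, weight and history of hypertension", as well as systolic pressure, diabetes, severity, age and others.

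Section 3.9 names no reference profile, joint distribution of attributes, prevalence weights or averaging step for this analysis. On the data source, section 3.3 refers to "real cases identified through SITS-UK (thrombolysed cases only", and sections 3.3 and 3.8 add local audit data with both treated and untreated cases.

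**The concern.** The label and the rule point to different quantities. A population-level impact is an average over the patients in some population. Changing one attribute with the rest held constant gives the effect for one combination of the other attributes or, if they are swept over their ranges, a span of such effects. A range carries no information on how common each combination is, so a sweep does not give an average either.

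This would not matter if an attribute's effect on the gain from treatment were the same in everyone. Here it generally is not. QALYs are built from probabilities of Rankin states, which are bounded, and from life expectancy, which depends on age. The protocol itself says in section 1.0, of outcomes and adverse effects, that "it is clear that these will vary from patient to patient (for example related to variations in blood pressure, age, stroke severity".

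At stake are the QALY figure for each attribute, the order of the attributes by that figure, and the marginal cost-effectiveness built on it. Sections 4.0 and 3.9 together imply that findings of this kind reach training material, the DASH II tutorial and guideline bodies. A profile-specific number read as a population figure could mislead there.

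**Working it through.** The protocol gives no QALY result, DASH II coefficient, link function or utility for this analysis, so no figure of its own can be reproduced. The check is an illustration under stated assumptions.

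**Assumed model.** Logistic, no interactions. Let x be the log-odds of a good outcome without treatment, as fixed by the held attributes. T is the treatment odds ratio and A the odds ratio for one step of the attribute under study.

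- Gain from treatment: g(x) = expit(x + ln T) − expit(x)
- Effect of the attribute on that gain: d(x) = g(x + ln A) − g(x)

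**Step 1: dependence on the held values** (T = 1.3, A = 0.6; extra good outcomes per 1,000 treated).

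- x = −1 (26.9% do well untreated): g = 323.5 − 268.9 = 54.6. With the attribute, 223.0 − 180.8 = 42.2. So d = −12.4.
- x = +1 (73.1% do well untreated): g = 779.4 − 731.1 = 48.4 (from unrounded values). With the attribute, 679.5 − 619.9 = 59.6. So d = +11.2.

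In this model d changes sign at x = −(ln T + ln A)/2. For T from 1.3 to 2.0 and A from 0.5 to 0.8, that is an untreated probability of 0.44 to 0.55.

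**Step 2: single profile against case-mix average.** Take x as normal around the same centres and average d(x) by numerical integration.

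| SD of x | Centre −1: average | Single profile ÷ average | Centre +1: average | Single profile ÷ average |
|---|---|---|---|---|
| 0.5 | −10.8 | 1.2 | +9.5 | 1.2 |
| 1.0 | −7.5 | 1.7 | +6.3 | 1.8 |
| 1.5 | −4.8 | 2.6 | +4.0 | 2.8 |
| 2.0 | −3.1 | 4.0 | +2.5 | 4.5 |

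The single central profile overstates the average by about 1.2 to 4.5 times. A second setting (T = 1.5, A = 0.5, centre 65%) gives +14.8 at the profile against averages of about +12.1 down to +2.9, or about 1.2 to 5 times.

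**Step 3: age.** With T = 1.5 and 50% doing well untreated, the gain in independence is 0.60 − 0.50 = 0.10. With an assumed utility gap of 0.4 and no excess early death, QALYs gained are 0.10 × 0.4 × life-years: 0.2, 0.4 and 0.8 for 5, 10 and 20 years. The age at which patients are held therefore rescales the QALY gain even when the outcome probabilities are unchanged.

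**Step 4: linked inputs.** If aspirin monotherapy and aspirin plus clopidogrel were two free yes/no inputs, one of their four combinations (both yes) could not occur. The protocol does not describe the coding.

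**The case against.** The case on the other side has real force in several places.

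- **No fixed profile is named.** A reader might infer that one reference patient is used throughout. The text refers to a range of levels and to individual patients, which could mean a sweep or observed registry values. This stands. The point is therefore that the rule gives conditional results and states no averaging, whichever reading is taken.
- **The detail may sit in an analysis plan that is not shown.** Averaging weights could be left to such a plan. But section 3.9 does more than stay silent: it states a rule, and that rule does not yield the quantity it announces.
- **One attribute at a time matches the choice experiment.** Section 1.1 explains that the design lets each attribute's effect on the choice be estimated separately. That is a reason to change one attribute at a time, and the fix below keeps this. It does not make the effect on QALYs the same at every profile.
- **Opposite signs.** A reader might infer that two analysts following the text would report opposite signs. That is possible in a non-additive model, but the documents do not show it for DASH II. Averaging does not remove it either: the two centres in step 2 keep opposite signs (−4.8 and +4.0 at SD 1.5). This is why the target population has to be stated. The sign in question is that of the attribute's effect on the gain, not whether treatment helps.
- **Impossible patients.** A reader might infer that the analysis will evaluate patients who cannot exist. That needs the two antiplatelet inputs to be coded as independent flags, which is not stated, and it needs antiplatelet use to be among the attributes varied. Diabetes with glucose held, or hypertension history with pressure held, gives unusual patients, not impossible ones, and the fix shares that feature.
- **The figures are assumed.** They count good outcomes, leave out death in steps 1 and 2, and rest on chosen odds ratios and SDs. This also stands, and it is why a range is given and not one factor.

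**Conclusion.** The concern holds in this form: the rule in section 3.9 is a one-way sensitivity analysis, its size depends on the held values, and it does not deliver the population-level impact that the same section promises. The marginal cost-effectiveness estimate inherits the problem.

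That conclusion rests on the text and on QALYs being built from bounded outcome probabilities and age-based life tables. It does not depend on the assumed odds ratios.

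The size is illustrative. The overstatement of about 1.2 to 4.5 times assumes a logistic model without interactions, a treatment odds ratio of 1.3, an attribute odds ratio of 0.6, a single central profile and a log-odds SD of 0.5 to 2. No figure specific to DASH II can be derived from the protocol. This is a secondary modelling analysis that can be corrected before it is run, so the change should be made, but it does not touch the choice experiment itself.

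**What to change.** In section 3.9, replace the rule with the following steps.

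1. State the target population. SITS-UK holds treated cases only, so an average over it describes treated patients. The local audit data hold treated and untreated cases. The text should say which population the average is meant to represent and how the sources are used.
2. For each individual record, run DASH II with and without thrombolysis at that patient's own values, at each level of the attribute under study, changing nothing else.
3. Average the QALY differences over the target population and report their spread. Build the marginal cost-effectiveness estimate on the same runs.
4. Handle antiplatelet use as one attribute with three mutually exclusive levels: none, aspirin alone, aspirin plus clopidogrel. Note as a limitation that changing diabetes or hypertension history alone leaves glucose or blood pressure at the recorded value.

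If complete individual records are not available, call the analysis a one-way sensitivity analysis, state the profiles at which the other attributes are held, and drop the population-level label.

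The cost is more runs of an existing model and a change of wording. It also requires complete individual records on the DASH II inputs. Sections 3.3 and 3.8 already plan to use individual cases from SITS-UK and local audit, but the protocol does not say that those records are complete for every input.
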